## 11. CLINICAL MANAGEMENT AND DATA COLLECTION:

Table 2: Summary of Study Protocol

VISIT	LOCATION	TIMING	QUESTIONNAIRE	MEASURES	SPECIMENS
V1	In-person, PCTRC	Start	AQI intake*, Intake, PA, ACT or CACT, PAQLQ, tobacco intake	Spirometry, FeNO, ht, wt	NEC, urine
V2	Telephone	W4, 4 wks post V3 (+/- 7d)	sRQ, AQI_f/u, PA, ACT or CACT.	-	-
V3	Telephone	W8, 4 wks post V3 (+/- 7d)	sRQ, AQI_f/u, PA, ACT or CACT.,	-	-
V4	Telephone	W12, 4 wks post V3 (+/- 7d)	sRQ, AQI_f/u, PA, ACT or CACT.	-	-
V5	Telephone	W16, 4 wks post V3 (+/- 7d)	sRQ, AQI_f/u, PA, ACT or CACT.	-	-
V6	Telephone	W20, 4 wks post V3 (+/- 7d)	sRQ, AQI_f/u, PA, ACT or CACT.	-	-
7V	In-person, PCTRC	W24, 4 wks post V3 (+/- 7d)	sRQ, AQI_f/u, PA, ACT or CACT.	Spirometry, FeNO, ht, wt	NEC, urine

Intake questionnaire (completed by parent); AQI intake- includes parent portion (completed by parent) + AQI follow up (completed by participant); PA=physical activity (parent and/or participant), ACT=asthma control test ages 12 and older (completed by participant); CACT=childhood asthma control test for ages 8-11 (completed by parent and participant); PAQLQ(s)-pediatric asthma quality of life questionnaire (completed by participant); participant tobacco intake form (completed by participant); sRQ= shortened respiratory questionnaire (completed by parent); AQI\_f/u=AQI follow up questionnaire (completed by participant).

Ht=height, wt=weight, NEC=nasal epithelial cells

\*AQI intake form should be completed prior to AQI education/intervention.

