## STATISTICAL PLAN:

Statistical Analysis: Data will be analyzed using SAS (SAS 9.4, Cary, N.C.). Baseline statistics per treatment group will be obtained. Bivariate analysis of covariates (age, sex, race/ethnicity, asthma severity, phenotype (i.e. atopic), socioeconomic status (SES), exposure to primary or secondary tobacco smoke, FeNO, use of controller medication, etc) between groups will be conducted using student t-test or Wilcoxon rank sum and Fisher's exact or Chi-square (where appropriate and based on distribution). Variables with significant differences between groups ( $P<0.05$ ) will be considered for inclusion in multivariate model selection. The effects of physical activity on the outcomes will be compared between groups. Baseline knowledge and usage of AQI will be assessed. Adherence to AQI will also be assessed and compared between groups, with potential stratification by AQI usage. Additionally, differences in weight and BMI will be assessed to evaluate if adherence to AQI promotes sedentarism and leads to increased weight gain. We will evaluate our outcomes (Aims 2 and 3) in three ways. First, we will evaluate the average difference (overall mean) between groups for our primary outcomes using T test or chi-square (where appropriate). Additionally, we will test the average mean difference between each treatment group by multivariate regression (linear for PAQLQ and ACT or CACT, and/or Poisson or logistic regression for mean asthma exacerbations depending on distribution) to allow for covariate adjustment. Second, we will use paired t-tests (or matched Wilcoxon signed-rank) to evaluate the within group effects (6 month mean – baseline) for each primary outcome. Third, to assess the effects over time in our intervention study (correlated repeat measures data), we anticipate analyzing our primary outcomes by generalized linear mixed models (GLMM). For these models, we will first evaluate the distribution of our primary outcome and determine the most appropriate link (e.g. for severe asthma exacerbations: logistic link if there are overall a high proportion of participants with none, or Poisson link if more consistent with count data). A stepwise approach will be used to build all multivariable models. All final models will include age, sex, race/ethnicity, SES, and tobacco smoke exposure. Additionally, the above outcomes will be stratified by age group (8-12y, 13-17y) to determine if the effects are greater in older children for whom the AQI recommendations may be better self-incorporated into outdoor physical activities, vs the younger group who will likely be more reliant on parental checking and activity modification.

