
Power calculations: Power calculations were conducted using G\*Power 354 and SAS (SAS 9.4, Cary, N.C.) using proc glmpower. For mean difference between treatment groups (routine vs. intervention) with sample size of 20 participants per group, two-tailed test, alpha 0.05, we will have  $\geq 90\%$  power to detect a mean difference of 1.05 between groups for mean asthma exacerbations, ACT and C-CACT, and PAQLQ. Our study will provide  $\geq 80\%$  power to detect a mean difference of 0.91. As the clinical difference for ACT is 2-3 points, we anticipate adequate power to detect a clinical difference. The estimated clinically meaningful difference in PAQLQ is 0.5, and our study may be underpowered to detect this small of difference with this analysis. For comparison within each treatment group, comparing the matched difference (end of study- baseline), using the same assumptions above, we will have  $\geq 90\%$  power to detect a mean difference of 0.76, and  $\geq 80\%$  power to detect a mean difference of 0.66. Therefore, we expect better ability to detect changes in PAQLQ within the groups than between them. For repeat measures, we estimated our power using proc glmpower using F test based on Hotelling-Lawley trace. We estimated a study allocation of 1:1, alpha 0.05, repeated measures at 1, 2, 3, 4, 5 months, lear correlation structure with base correlation 0.85 & decay rate of 1, with an estimated mean difference of 2, standard deviation of 2, which provides a  $\geq 90\%$  power for a treatment group size of 12 for overall mean and n=26 for time\*treatment.

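### The Poisson branch of the covariate-adjusted exacerbation regression has no provision for overdispersion, so its p-values and intervals are probably too optimistic

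*Combined protocol and SAP*

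**What the plan says.** The Statistical Plan evaluates the outcomes of Aims 2 and 3 in three ways.

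- **Between arms.** An unadjusted comparison "between groups for our primary outcomes using T test or chi-square (where appropriate"), followed by a covariate-adjusted regression. For exacerbations that regression is "Poisson or logistic regression for mean asthma exacerbations depending on distribution".
- **Within arms.** Paired tests of change from baseline.
- **Over time.** For the repeated data, "we anticipate analyzing our primary outcomes by generalized linear mixed models (GLMM"). Here "we will first evaluate the distribution of our primary outcome and determine the most appropriate link", the example being "logistic link if there are overall a high proportion of participants with none, or Poisson link if more consistent with count data". The random effects are not stated.

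On covariates, "A stepwise approach will be used to build all multivariable models". Every final model carries age, sex, race/ethnicity, SES and tobacco smoke exposure. Asthma severity is on the list compared between arms at baseline, and is considered for a model only if the arms differ on it at P<0.05.

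The Statistical Plan and its power paragraph do not mention overdispersion, a scale parameter, a negative binomial model, robust variance, a follow-up-time offset or incomplete follow-up. No single analysis is named as primary.

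**The concern.** A Poisson regression takes the variance of each child's count to equal its mean, given the covariates. If children differ in underlying rate for reasons outside the model, the variance is larger and the model's standard errors are too small by the square root of the variance-to-mean ratio.

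Four features of the documents make this likely:

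- Section 5.1 admits all grades of persistent asthma.
- Section 2.1 (Aim 2) lists severity among the known contributors to exacerbations, yet it is not a forced covariate.
- The Statistical Plan foresees that many children may have no severe event, while section 10.1 provides for children with more than three. Many zeros with a long upper tail is the overdispersed pattern.
- The Statistical Plan itself treats a child's repeated measurements as correlated.

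At stake is the adjusted treatment effect for Aim 2. It could be reported as significant, or with a narrow interval, when the data do not justify it.

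**Working it through.** **1. The plan's own figures.** The power paragraph works "with sample size of 20 participants per group, two-tailed test, alpha 0.05". A two-sample t-test with 38 degrees of freedom and an SD of 1 (assumed, because none is stated) has noncentrality d × √(20/2).

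- d = 1.05: 1.05 × 3.162 = 3.32, power 89.9%.
- d = 0.91: 0.91 × 3.162 = 2.88, power 80.1%.

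These match the stated 90% and 80%. They describe a t-test on a standardised difference and say nothing about how the Poisson model behaves.

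**2. How large might the dispersion be?** The documents give no rate or variance, so a range is needed. As a guide, suppose six monthly counts are each roughly Poisson with mean m and have within-child correlation ρ. The six-month total has mean 6m and variance 6m(1 + 5ρ), so the variance-to-mean ratio is φ = 1 + 5ρ. Then ρ = 0.1 gives 1.5, ρ = 0.2 gives 2 and ρ = 0.4 gives 3. These ρ values are assumptions.

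**3. Closed form.** The true two-sided error of a nominal 5% Poisson Wald test is 2 × [1 − Φ(1.96/√φ)].

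| φ | Type I error | 95% interval coverage | Width factor needed, √φ |
|---|---|---|---|
| 1 | 5.0% | 95.0% | 1.00 |
| 1.25 | 8.0% | 92.0% | 1.12 |
| 1.5 | 11.0% | 89.0% | 1.22 |
| 2 | 16.6% | 83.4% | 1.41 |
| 3 | 25.8% | 74.2% | 1.73 |

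**4. Simulation without covariates.** 20 per arm, no true effect, gamma-Poisson counts, 40,000 trials per setting. Entries are rejection rates.

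| Mean events | φ | Plain Poisson | Pearson scale, t reference | t-test | Logistic (any event) |
|---|---|---|---|---|---|
| 0.5 | 1.0 | 4.2% | 3.8% | 4.9% | 4.1% |
| 0.5 | 1.5 | 9.3% | 3.8% | 4.6% | 4.2% |
| 1.0 | 1.0 | 4.5% | 4.3% | 4.8% | 4.0% |
| 1.0 | 1.5 | 10.3% | 4.6% | 4.8% | 3.9% |
| 1.0 | 2.0 | 15.6% | 4.6% | 4.7% | 3.8% |
| 2.0 | 1.0 | 4.7% | 4.6% | 4.8% | 0.6% |
| 2.0 | 2.0 | 16.3% | 5.0% | 4.9% | 3.6% |
| 2.0 | 3.0 | 25.3% | 4.9% | 4.6% | 4.1% |

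A Poisson model with a child random intercept, fitted to each child's total and tested by likelihood ratio, rejected 5.5-6.3% in overdispersed settings (400 trials each, Monte Carlo standard error about 1.2 points).

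**5. Simulation with covariates.** This is closer to the planned model: arm plus five covariates unrelated to outcome, means 0.5 to 2.

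- Plain Poisson: about 4% at φ = 1, 10-12% at 1.5, 14-16% at 2, 21-26% at 3.
- Pearson scale with t reference: about 4-6%.
- Robust variance with t reference: 7-12%.
- Negative binomial (means 1-2, φ 1.5-2): 5.4-7.7%, with 6-23% of fits not converging.

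**6. Model choice.** Taking logistic when more than 50% of all children are event-free (an assumed threshold, arms pooled) and Poisson otherwise gave 3.9-4.7% without overdispersion. With overdispersion the result never exceeded the plain Poisson rate in the same setting. Counting either model as a success gave 5.1-6.9% even without overdispersion.

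**7. Offset.** Mean 1 event, no overdispersion.

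- 15% dropout in both arms: 5.2% without an offset, 4.5% with one.
- 25% against 5% dropout: 6.5% without, 4.6% with. If dropout times are uniform, mean exposure is 0.875 and 0.975 of full follow-up, and ln(0.875/0.975) = −0.11. That is the bias in the log rate ratio, and the simulation gave −0.113.

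**The case against.** The strongest reply is that this is one of several between-arm analyses in a 40-child pilot, and that the plan names a model family rather than its fitting options. Much of that stands, and it rules out several stronger readings.

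- **That the whole exacerbation comparison is too optimistic.** A reader might infer this, but the t-test held 4.4-4.9% across all simulated settings, and a random-intercept mixed model was close to nominal. The plan does not, however, say that its mixed model has that term.
- **That the logistic branch shares the fault.** One yes/no result per child cannot be overdispersed in this sense, and it rejected 0.6-4.3%.
- **That choosing the model from the data narrows the intervals.** The stated criterion refers to participants overall, which reads as pooled over arms, and such a choice added no error. The unquantified threshold is a separate matter: it leaves open whether an odds ratio or a rate ratio is reported.
- **That the missing offset causes the optimism.** Planned follow-up is equal. The Table 2 entry for the last visit, "W24, 4 wks post V3 (+/- 7d"), allows 7 days in 168, about 4%. An offset matters only with dropout or missed calls, and then mainly as bias when these differ by arm.
- **That the inflation is established.** It is conditional on a variance-to-mean ratio above 1, which the documents cannot confirm.

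What does not stand is the idea that the other analyses rescue this one. The adjusted regression is a separate estimate and will be read on its own. Silence on dispersion leaves the default, which has none.

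**Conclusion.** The point holds for the Poisson branch of the covariate-adjusted regression, and only there. As written, that analysis has no protection against overdispersion, and the enrolled population and forced covariate list make overdispersion probable. For assumed variance-to-mean ratios of 1.5, 2 and 3, type I error is about 10-12%, 14-16% and 21-26% against 5%; at a ratio of 1 there is none. The figures rest on gamma-Poisson counts, 20 per arm, means of 0.5 to 2 events and covariates unrelated to outcome. The size in this trial cannot be fixed from the documents. The change should be made because it is cheap and loses little if the counts turn out to be Poisson.

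**What to change.** In the Statistical Plan:

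1. Specify the adjusted count regression as Poisson with a Pearson dispersion scale and a t reference, with arm and age stratum as terms. Do not offer small-sample robust variance or negative binomial as equivalents with 20 per arm: in the checks above they rejected more often, and the negative binomial often failed to converge.
2. State that the mixed model includes a child random intercept.
3. As secondary points, name the rate ratio in advance as the effect measure, keep logistic regression of any exacerbation as a sensitivity analysis, and add log follow-up time as an offset to cover dropout or missed calls.

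The cost is plan wording and one software option, with a check that the output uses t rather than the normal distribution. Intervals widen by about √φ. If φ = 1, the cost is only the t multiplier: with seven coefficients and 40 children, 33 degrees of freedom give 2.03 against 1.96, about 4% wider.

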### 2.1 Hypothesis and Specific Aims

We hypothesize that the addition of the AQI to AAP will (A) reduce asthma exacerbations, and (B) improve symptom control & quality of life in children with asthma. To test these hypotheses, in this study we will pursue the following specific aims:

- Aim 1: To recruit a pilot cohort of 40 children with asthma. For proof of concept, we will recruit 40 children with asthma from Children's Hospital of Pittsburgh, the only children's hospital serving southwest Pennsylvania (metropolitan area >2.6 million people). Baseline knowledge about the AQI including familiarity, usage, and prior healthcare provider discussion will be assessed.

- Aim 2: To evaluate if the addition of the AQI to AAP reduces asthma exacerbations in a pilot study of children. Participating children (Aim 1) will be randomized to one of two groups. All participants/caregivers will receive an AAP and verbal AQI education. The intervention group will additionally demonstrate the ability to check the AQI, and AQI recommendations will be incorporated onto their written AAP. Children will be followed monthly for 6 months to evaluate adherence to AQI recommendations and assess the frequency of asthma exacerbations, defined per ATS guidelines. Other known factors contributing to asthma exacerbations, such as asthma severity, viral illnesses, allergic triggers will also be monitored.
- Aim 3: To examine whether the addition of the AQI to AAP improves asthma symptom control and quality of life in a pilot study of children. Asthma symptom control will be measured in participating children monthly, and quality of life will be assessed before randomization and at 6 months. Symptom control and quality of life will be evaluated within (before/after intervention) and between groups.

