## 2.3 Questionnaires

7 questionnaires will be administered to the parents and children of study participants (see Figure 4). (1) Intake Questionnaire: this is a respiratory/general health questionnaire used by the [REDACTED] Study. (2) Tobacco Questionnaire- this is a short questionnaire from questions used on the National Youth Tobacco Survey. (3) AQI intake & follow up: Intake: there are no existing questionnaires evaluating what parents know about the AQI as pertains to their children with asthma. This questionnaire contains questions from NHANES and BRFSS with modifications. The AQI intake has a section to be completed by the parent to understand the parent's knowledge and practices regarding the AQI. The

intake questionnaire additionally contains a section for the child to complete, which is the AQI follow up questionnaire. The follow up questionnaire was developed by the PI to assess usage of the AQI. **(4)** Asthma Control Test (ACT) and Childhood Asthma Control Test (C-ACT) are validated questionnaires to assess asthma control in the last 4 weeks. **(5)** Pediatric Asthma Quality of Life Questionnaire (PAQLQ(S)) is validated questionnaire that will be interviewer-administered. **(6)** Physical activity questionnaire contains modified questions from NHANES and The Physical Activity Questionnaire for older children and adolescents. **(7)** Shortened respiratory questionnaire (sRHQ): this is a short questionnaire that has been modified from the [REDACTED] study. It is designed to capture asthma exacerbations.

The order of the questionnaires is important. The AQI intake form will be completed by the parent/guardian and the child participant prior to AQI education/intervention.

**2.4 Lung Function Tests:** Spirometry and fractional exhaled nitric oxide (FeNO) will be obtained at entrance and exit visit as secondary measures of control (e.g. forced vital capacity (FVC), forced expiratory volume in 1 sec (FEV1), and FEV1/FVC).

**2.5 Anthropometric measures:** Height and weight will be obtained at the baseline and exit visit, to assess if adherence to AQI potentially alters weight/BMI by increased sedentarism.

**2.6 Urine collection:** as an ancillary to this study, will collect urine for cotinine measurement (nicotine metabolites) and store.

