**Plan activities when and where pollution is lower:**

- Ozone is usually higher on hot summer days in the afternoon & early evening. On days ozone is high, plan your outdoor activities in the morning.
- Particulate pollution can be higher in certain places. Try to avoid exercising where particles are higher. Examples: near busy roadways, during rush-hour traffic, near industrial areas, and when there is smoke in the air.

*Don't let asthma keep you from being active. The CDC recommends 60 minutes of physical activity a day. If asthma is limiting your activity, talk to your doctor!*

Table 1: Study Procedures

VISIT	LOCATION	QUESTIONNAIRE	EMR	MEASURES	SPECIMENS
1	In-person, PCTRC	Intake, AQI intake, PA, ACT or CACT, PAQLQ, tobacco intake	Confirm asthma controller medications, IgE, allergen testing, eosinophils, BAL or sputum eosinophils	Spirometry, FeNO, height, weight	Nasal epithelial cells, urine
2	Telephone	sRQ, AQI_f/u, PA, ACT or CACT.	-	-	-
3	Telephone	sRQ, AQI_f/u, PA, ACT or CACT.,	-	-	-
4	Telephone	sRQ, AQI_f/u, PA, ACT or CACT.	-	-	-
5	Telephone	sRQ, AQI_f/u, PA, ACT or CACT.	-	-	-
6	Telephone	sRQ, AQI_f/u, PA, ACT or CACT.	-	-	-
7	In-person, PCTRC	sRQ, AQI_f/u, PA, ACT or CACT.	-	Spirometry, FeNO, height, weight	Nasal epithelial cells, urine

Intake questionnaire (completed by parent); AQI intake- includes parent portion (completed by parent) + AQI follow up (completed by participant); PA=physical activity (parent and/or participant), ACT=asthma control test ages 12 and older (completed by participant); CACT=childhood asthma control test for ages 8-11 (completed by parent and participant); PAQLQ(s)-pediatric asthma quality of life questionnaire (completed by participant); participant tobacco intake form (completed by participant); sRQ= shortened respiratory questionnaire (completed by parent); AQI\_f/u=AQI follow up questionnaire (completed by participant).

**8.1a Questionnaires:** the risks from questionnaire administration involves social-psychological risk resulting from inadvertent disclosure of medical information and/or questions may create discomfort. Participants and parents do not have to answer any question that they do not wish to answer.

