## **11.2 Eligibility and Randomization (Visit 1)**

Once the family and participant have indicated willingness to participate and have scheduled a V1, the research coordinator will notify PI. PI will review medical record (granted permission by Asthma Registry patients and allowable access as part of regular duties) to confirm asthma controller medications. PI will prepare AAP for research coordinators to distribute. In the event of a discrepancy between parental reported controller medication and medical record medication, the PI will reach out (with participant parent permission) to healthcare provider managing asthma to confirm asthma controller medications.

After informed consent has been obtained, participant's will be randomized 1:1 by age group. The RC assign random group at time of intervention. Eligibility for lung function tests and/or NEC will be assessed prior to study procedures. Questionnaires will be administered, height and weight will be obtained, lung function tests will be obtained (if eligible), specimens will be collected (if applicable), and AQI education will be provided. For the intervention group only, the AAP containing the AQI information will be provided. The intervention group will demonstrate ability to navigate to either airnow website or airnow app on smart phone. For the control group, an AAP will be provided (containing no AQI information) Both the participants, parents, and research coordinator will know randomization assignment. V1 should not be done if child participant has been sick with respiratory infection in prior 7 days or currently has respiratory symptoms.

If a participant's spirometry demonstrates an FEV1 <80%, the family and participant's managing asthma healthcare provider will be notified. Per family permission, spirometry will be shared with managing asthma healthcare provider. If a participant's FeNO is above 20ppb, with family permission, FeNO will be shared with managing asthma healthcare provider.

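### The paired test against baseline is planned for exacerbations too, but no baseline exacerbation count, recall window or scaling is defined

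*Combined protocol and SAP*

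**What the plan says.** The Statistical Plan opens its outcome analyses with "We will evaluate our outcomes (Aims 2 and 3) in three ways". The second way reads "we will use paired t-tests (or matched Wilcoxon signed-rank) to evaluate the within group effects", and the contrast is given as "6 month mean – baseline) for each primary outcome".

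Exacerbations are the subject of Aim 2 (section 2.1): "Aim 2: To evaluate if the addition of the AQI to AAP reduces asthma exacerbations in a pilot study of children". The power section lists them with ACT/C-ACT and PAQLQ. There is no formal list of primary outcomes, but nothing exempts exacerbations from the paired test.

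Section 2.3 says of the shortened respiratory questionnaire (sRHQ there, sRQ in the tables; I take them to be the same form): "It is designed to capture asthma exacerbations". Table 1 lists the V1 questionnaires as "Intake, AQI intake, PA, ACT or CACT, PAQLQ, tobacco intake". Table 2 lists the same set in a different order. Both tables give the sRQ at every visit from V2 to V7 and not at V1.

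For before/after comparison, Aim 3 names only two outcomes: "Symptom control and quality of life will be evaluated within (before/after intervention) and between groups".

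**The concern.** A paired test needs two measurements of the same quantity on each child. For exacerbations the follow-up measurement is defined: events under section 2.2, reported about every four weeks on the sRQ for 24 weeks. The baseline measurement is not. The analyst would have to choose, after the data are in, where the baseline count comes from, how far back it reaches and whether to rescale it.

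That choice can decide the result. Exacerbations are counts, and a count grows with the length of time observed. A year of recall set against 24 weeks of follow-up looks like improvement in both arms; four weeks of recall looks like deterioration. A decrease of this kind in the intervention group could be read as an effect of the AQI plan.

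There is also a missed opportunity. The trial enrols 40 children with mild, moderate or severe persistent asthma, and exacerbation history is not among the covariates named in the Statistical Plan.

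**Working it through.** **1. The plan's own figures.** The within-group power statement (20 per group, two-sided alpha 0.05) gives at least 90% power at a mean difference of 0.76 and at least 80% at 0.66. No standard deviation is stated; I take the SD of the paired difference as 1. For a paired t-test with df = 19, the noncentrality is d × √20:

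- d = 0.76: 0.76 × 4.472 = 3.40, power 89.7%
- d = 0.66: 0.66 × 4.472 = 2.95, power 79.9%

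The figures reproduce as standardised differences. The power arithmetic is not the problem; for exacerbations, the baseline term of the difference is.

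**2. Which outcomes have a scheduled pair?** From Tables 1 and 2:

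| Outcome | V1 | V7 | Before/after named in the aims |
|---|---|---|---|
| ACT/C-ACT | yes | yes | yes (Aim 3) |
| PAQLQ | yes | not listed, though Aim 3 says it is assessed at 6 months | yes (Aim 3) |
| Exacerbations (sRQ) | not listed | yes, and at V2 to V6 | no (Aim 2) |

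**3. Other possible V1 sources.** The record review in Table 1 covers controller medications, IgE, allergen testing and eosinophils, but not exacerbation history. The intake form is described only as a respiratory and general health questionnaire. Section 11.3 places the exacerbation questions on the monthly questionnaires. None of these supplies a defined baseline count.

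**4. What an unscaled window mismatch does.** This is an illustration on assumed values, none of them in the documents: Poisson counts, one common annual rate r, no true change, independent periods, 20 children and raw counts compared. The expected spurious change is r × (24 − w)/52, where w is the look-back in weeks. The false rejection rate of the paired t-test comes from 20,000 simulated groups per row.

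| Events per year | Look-back | Spurious mean change | False rejection |
|---|---|---|---|
| 0.5 | 12 months | 0.5 × (−28/52) = −0.27 | 26% |
| 1 | 12 months | −0.54 | 48% |
| 2 | 12 months | −1.08 | 78% |
| 0.5 | 4 weeks | 0.5 × (20/52) = +0.19 | 32% |
| 1 | 4 weeks | +0.38 | 64% |
| 2 | 4 weeks | +0.77 | 92% |

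The nominal rate is 5%. Converting both counts to rates would remove the mean shift under these assumptions, but the plan states no such conversion.

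**5. Possible gain from a baseline covariate (illustration only).** If the baseline and follow-up counts correlate at r = 0.3 to 0.6 (assumption), a linear model's residual variance falls by r² = 9% to 36%. The equivalent sample size is 40/(1 − r²) = 44 to 62.5. The plan uses Poisson or logistic models for exacerbations, where the gain may differ. It would also be net of the covariates already in the final models.

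**The case against.** The strongest reply is that this is loose drafting in a secondary, non-randomised contrast. Aim 2 is a between-group question. The plan's first approach (between-group test and regression) and third approach (mixed models on follow-up data) need no baseline count. Aim 3 restricts before/after comparison to control and quality of life, and the within-group power discussion names only PAQLQ. All of this stands. It limits the consequence, but the Statistical Plan still commits to the test for every primary outcome.

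A second reply is that the intake form may share items with the sRQ. Both are described as drawn from a study whose name is redacted, and the follow-up form is called a shortened one. This also stands. A reader might infer from the tables that no exacerbation history is taken at V1, or that the paired test cannot be computed at all. The documents do not show either, because the items of neither form are given. They show only that a matching baseline is not specified.

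A reader might also infer a baseline biased towards event-free children from section 11.2: "V1 should not be done if child participant has been sick with respiratory infection in prior 7 days" or has current respiratory symptoms. The text does not support that. The infection rule concerns 7 days, which is 7/28 = 25% of a four-week window and about 7/182 = 4% of a six-month one. Exacerbations can still fall in the remainder.

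Finally, a six-month recall at V1 would not match monthly reporting either. That is correct, and is why the count is proposed as a covariate and not as a paired baseline. A covariate need only be measured in the same way in both arms.

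**Conclusion.** The point holds as an internal inconsistency that should be corrected. A pre-specified paired test of exacerbations has no defined baseline measure, window or scaling, and the form that captures the outcome is not scheduled at V1. The between-arm exacerbation analyses remain valid.

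The size of the possible error depends on how the gap would be filled. The 26% to 92% false rejection rates apply only if raw counts from a 12-month or four-week look-back were used, under the assumed event rates and a simple Poisson model. They show that the choice matters; they do not predict what this trial would report.

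It would be tempting to say the trial forgoes the equivalent of 4 to 22 children for want of a baseline count. The documents do not support that as a finding. The figure rests on an assumed correlation and a linear-model formula, ignores covariates already adjusted for, and concerns the between-arm analysis, not the paired test.

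**What to change.** 1. In the Statistical Plan, replace the reference to each primary outcome in the paired analysis with ACT/C-ACT and PAQLQ. This agrees with Aim 3, loses no stated objective and needs no new data. It resolves the inconsistency by itself.
2. For the PAQLQ paired test to have its second value, Tables 1 and 2 should list PAQLQ at V7, as Aim 3 implies.
3. Add to V1 in both tables an exacerbation count using the section 2.2 definitions and a fixed look-back, for example 6 months, asked with the sRQ items before randomisation is revealed. If the intake form already has equivalent items, say so and state their window.
4. Pre-specify that count as a covariate in the between-arm exacerbation model, and not as the baseline of a paired difference. Fixing it in advance also keeps it out of the stepwise selection.

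Items 1 and 2 are text edits, plus one PAQLQ interview at V7 if it is not already intended. Items 3 and 4 cost a few minutes of parent time at a visit already held, and the recall is longer and so less reliable than on the monthly form. If the sponsor declines items 3 and 4, item 1 is still needed.
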